### 6.3 PATIENT SETS ANALYSED

The Screened Set (SCR) includes all patients who signed the informed consent form and will be used to summarize patient disposition.

The Run-In Set (RIS) includes all patients who received at least one dose of ibrutinib. The RIS will be used for the analysis of exposure to ibrutinib.

The Treated Set (TS): consists of all patients who received at least one administration of BI 836826. The TS will be used for all planned safety and efficacy analyses.

The MTD evaluation set: This patient set includes all patients who were documented to have received at least one dose of BI 836826 and were not replaced for the MTD evaluation. The MTD evaluation set will be used for the primary analyses of DLTs and MTD determination.

Rules for replacement of patients are defined in Section 3.3.4.1 of the CTP. The list of replaced patients will be provided by the Trial Clinical Monitor (TCM) no later than the last blinded report planning meeting (BRPM) and will be stored in the TMF.

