3.3.4 Removal of patients from therapy or assessments

3.3.4.1 Removal of individual patients

An individual patient may be withdrawn from BI 836826 trial treatment if:

- Disease progression as assessed by investigator
- Initiation of any other new anticancer therapy for CLL, in the absence of disease progression
- The patient withdraws consent for study treatment or study participation, without the need to justify the decision.
- The patient is not able to tolerate a second re-challenge for the same AE (see [Section 4.1.4.5](#))
- The patient needs to take concomitant drugs that interfere with BI 836826, ibrutinib, or the trial results evaluation (see [Section 4.2.1](#) and [4.2.2](#))
- The patient can no longer be treated with trial medication for other medical reasons (such as another severe intercurrent illness, pregnancy, or breastfeeding)

In the last two cases, consultation with the BI Clinical Monitor is recommended.

Given the patient's agreement, the patient will undergo the procedures for early treatment discontinuation and follow up as outlined in the [Flow Chart](#) and [Section 6.2.3](#).

For all patients the reason for withdrawal (e.g. adverse events) must be recorded in the eCRF. These data will be included in the trial database and reported.

All withdrawals will be documented and the reason for withdrawal recorded and discussed, as necessary in the final report of the trial. As soon as a patient is withdrawn from the trial, the next scheduled visit and the EOT have to be performed if feasible. Every effort should be made to follow-up patients in case an AE is still ongoing at the time of withdrawal.

If a patient should become pregnant during the trial, the combination treatment must immediately be interrupted. The patient will be followed up until delivery or termination of pregnancy (see [Section 5.3.7](#)). The data of the patient will be collected and reported in the Clinical Trial Report (CTR) until last patient last visit and any events occurring thereafter will be reported in BI drug safety database.

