#### **5.2.2 Other secondary endpoints**

The secondary endpoint is the MTD. The MTD may be considered reached if the posterior probability that the true DLT rate is in the target interval  $[0.16, 0.33)$  is larger than 0.5 or if at least 15 patients have been treated in the Phase Ib part, of which at least 6 at the MTD. Patients who have been replaced are not considered evaluable for MTD determination. Only DLTs occurring in the MTD evaluation period will be considered for the determination of the MTD

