### 6.2 IMPORTANT PROTOCOL VIOLATIONS

No per protocol set analysis will be performed for this study, hence no patient will be excluded from the analyses. However, patients with important protocol violations (IPVs) will be documented. The following table defines the different categories of IPVs.

Table 6.2 : 1 Important protocol violations

| Category / Code   | Description   | Example/Comment  | Excluded from |
|-------------------|---|--|---------------|
| A          | Entrance criteria not met  |  |               |
| A1 a   | Patient has condition that may cause additional risk from study medication    | Check Inclusion/Exclusion criteria:
In6, In8
Ex4, Ex9, Ex10, Ex11, Ex12, Ex13, Ex16,
Ex17, Ex18, Ex19 | None          |
| A2 a   | Patient has laboratory assessments that may cause additional risk             | Check whether baseline laboratory data comply with thresholds as defined by In7 and check that In7 = “Yes”     | None          |
| A3 a   | Patient is unable to comply with the protocol                                 | Check Ex20   | None          |
| A4 a+m | Patient does not have trial diagnosis or is not part of the target population | Check Inclusion/Exclusion criteria:
In1, In2, In3, In4, In9, In10
Ex1, Ex3, Ex5, Ex6, Ex7                | None          |
| B          | Informed consent   |  |               |

Table 6.2 : 1 Important protocol violations (cont.)

|          |                   |   |  |      |
|----------|-------------------|---|--|------|
|          | B1 a   | Informed consent not given or too late                | Check In12
Check date of IC against date of Screening visit   | All  |
| C |                   | Trial medication and randomisation             |  |      |
|          | C1 a+m | Drug not administered according to protocol           | Infusion schedule followed = “No” and medical review of associated comments  | None |

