|          | C2 a   | Drug administration not according to schedule         | Ibrutinib not administered continuously from start of Run-in period
Cycle 1: pre-dose of 10 mg of BI836826 not administered on Day 1 and 50% of target dose on Day2 and Day 8 and 100% of target dose on Day 15.
Cycles 2-4: 100% of target dose of BI836826 not administered on days 1 and 15 of each cycle
Cycles 5-24: 100% of target dose of BI836826 not administered on day 1 of each cycle | None |
|          | C3 a   | Incorrect treatment taken                             | Study drugs dispensing error leading to change in actual treatment   | None |
| D |                   | Concomitant medication                         |  |      |
|          | D1 a+m | Prohibited medication                                 | 
 
• anti-neoplastic therapy
 
• long-term use (>7 days)of strong CYP3A inhibitor (check also Ex15)
 
• Oral anti-coagulants (check also Ex14)
 
 ongoing systemic immunosuppressive therapy other than corticosteroids (check also Ex8)  | None |
|          | D2 a+m | Pre-medication not administered according to protocol | Did the subject receive standard pre-medication = “No” to any standard pre-medication and medical review of associated comments – only until cycle 6, afterwards pre-medication according to investigator judgement  | None |

a = automated IPV; m = manual IPV; In = Inclusion criterion; Ex = Exclusion criterion

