## **7.4 PRIMARY ENDPOINTS**

The primary endpoints are the RP2D and the number of patients with DLTs in the MTD evaluation period. The number of patients with DLTs at each dose level will be presented for the MTD evaluation period for the MTD evaluation set and for the whole on-treatment period for the treated set separately.

The RP2D will either be the MTD or any lower dose, examined based on safety and efficacy criteria. The analysis of the MTD is based on a BLRM guided by the EWOC principle. Estimation of the MTD during the dose escalation phase of the study will be based upon the estimation of the posterior probability of the incidence of DLT in toxicity categories during the MTD evaluation period for all evaluable patients. The model to be used is specified in CTP Section 7.

The posterior probabilities that the toxicity rates of each dose level fall into the categories specified in CTP Section 7 estimated from the BLRM will be displayed graphically as well as in a table. This will be done for the MTD evaluation period as well as for the complete on-treatment period.

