### **7.5.2 Other Secondary endpoints**

The secondary endpoint is the MTD. This will be analysed analogously to the primary endpoint RP2D. Only patients evaluable for MTD determination will be used for the analysis of the MTD, i.e. patients, if any, who were replaced during the MTD evaluation period will be excluded from the analysis of the MTD.

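### SAP 6.3 defines the MTD evaluation set by absence of replacement, not by the protocol's evaluability criteria, and cites a protocol section that contains no replacement rule

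*SAP*

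**What the plan says.** SAP 6.3 defines the MTD evaluation set as patients who "received at least one dose of BI 836826 and were not replaced for the MTD evaluation" and uses it for the primary DLT analysis and for determining the MTD. It adds: "Rules for replacement of patients are defined in Section 3.3.4.1 of the CTP". The list of replaced patients comes from the trial clinical monitor. Protocol 3.3.4.1 opens "An individual patient may be withdrawn from BI 836826 trial treatment if" and goes on to withdrawal reasons, documentation and pregnancy. It says nothing about replacement.

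The evaluability rule is in protocol 3.1 and 5.3.6.2. A patient counts after a Cycle 1 DLT, or after receiving every planned Cycle 1 infusion of BI 836826 and at least 80% of ibrutinib doses. Anyone else stays in the safety analysis and is replaced for the MTD evaluation. Protocol 7.3 limits MTD determination to evaluable patients.

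Elsewhere the SAP uses two vocabularies. Section 5.2.2 says "Patients who have been replaced are not considered evaluable for MTD determination". Section 7.5.2 starts from evaluable patients, who "will be used for the analysis of the MTD, i.e. patients, if any, who were replaced during the MTD evaluation period will be excluded". Section 7.4 fits the model to DLTs "during the MTD evaluation period for all evaluable patients". None of these sections states the exposure criterion.

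**The concern.** Evaluability is a property of the patient: what was received and what happened in Cycle 1. Replacement is an operational event that depends on someone else being enrolled. A set defined by the second matches the first only if every non-evaluable patient really is replaced.

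That is no longer assured. Protocol 2.1 says recruitment stops, so a patient who falls short of minimum exposure late in the trial may have no successor. Under-exposure is foreseeable: protocol 6.1 has a Day 15 dose omitted when it would be delayed by more than a week, and protocol 3.1 requires four infusions, including that one. A programmer who follows SAP 6.3 literally would keep such a patient as a full DLT-free observation, and the one cross-reference offered would not correct this. At stake are the denominator of a primary endpoint and the posterior probabilities that SAP 7.4 promises to report.

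**Working it through.** **1. Membership under each rule**

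| Dosed patient | Protocol 3.1, 5.3.6.2, 7.3 | SAP 6.3, literal |
|---|---|---|
| Cycle 1 DLT | in | in |
| No DLT, minimum exposure met | in | in |
| No DLT, under-exposed, replaced | out | out |
| No DLT, under-exposed, not replaced | out | in, as DLT-free |

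Only the last row differs.

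**2. Size from the protocol's own table.** Table 10.7:1 gives the probability of overdosing at 200 mg as 0.144 after 0/2 DLTs at 100 mg (scenario 4) and 0.119 after 0/3 (scenario 1). One extra DLT-free patient lowers it by 0.144 − 0.119 = 0.025.

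**3. Size in the other scenarios.** Inputs are the priors in Table 7.1:3, the binomial likelihood in protocol 7.1 and the data in Table 10.7:1. The method is importance sampling with 3 million prior draws. Each draw is weighted by the product over doses of π^r(1−π)^(n−r), and the probability of overdosing is the weighted share of draws with π ≥ 0.33.

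The interaction printed in protocol 7.1 contains log(420/420) = 0, so it vanishes at the ibrutinib dose used. It gives a prior overdose probability of 0.208 at 200 mg, against 0.241 in Table 7.1:4. A product form, η(d1/200)(d2/420), gives 0.242 and reproduces all 18 usable next-dose values in Table 10.7:1 within 0.009. I use it below as an inferred form. It does not match everything: at the starting dose it implies exp(1.96 × 0.56 × 0.5) = 1.73-fold on the odds, not the 1.4-fold stated in 7.1.

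I took every scenario with a last cohort of three and a tabulated next dose. That is 18 scenarios and 17 distinct states, since 8 and 11 both pool to 2/6 at 100 mg. I then removed one DLT-free patient from the last cohort. Entries are the probability of overdosing at the tabulated next dose.

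| Scenario | Protocol | Re-run, patient counted | Re-run, patient left out | Difference |
|---|---|---|---|---|
| 1 | 0.119 | 0.116 | 0.145 | 0.029 |
| 2 | 0.174 | 0.180 | 0.257 | 0.077 |
| 5 | 0.248 | 0.241 | 0.273 | 0.032 |
| 6 | 0.163 | 0.162 | 0.222 | 0.060 |
| 7 | 0.141 | 0.143 | 0.206 | 0.063 |
| 8, 11 | 0.227 | 0.218 | 0.288 | 0.070 |
| 9 | 0.200 | 0.196 | 0.233 | 0.037 |
| 13 | 0.209 | 0.208 | 0.257 | 0.049 |
| 14 | 0.125 | 0.129 | 0.216 | 0.087 |
| 15 | 0.218 | 0.216 | 0.254 | 0.038 |
| 16 | 0.194 | 0.187 | 0.262 | 0.075 |
| 17 | 0.223 | 0.222 | 0.260 | 0.038 |
| 18 | 0.206 | 0.197 | 0.257 | 0.060 |
| 19 | 0.126 | 0.130 | 0.175 | 0.045 |
| 20 | 0.201 | 0.198 | 0.388 | 0.190 |
| 21 | 0.084 | 0.082 | 0.116 | 0.034 |
| 22 | 0.127 | 0.126 | 0.245 | 0.119 |

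The median difference is 0.060, and 15 of the 17 lie between about 0.03 and 0.09. The exceptions, 20 and 22, have two DLTs in three patients at a high last dose. Under the printed interaction the differences run from 0.026 to 0.143, median 0.047. A patient in an earlier cohort matters less: 0.000 to 0.056, median 0.012, over 24 scenario-cohort pairs (product form).

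**4. Crude rate.** The DLT count does not change but its denominator does. In scenario 18 at 200 mg, 2/5 = 40.0% becomes 2/6 = 33.3%.

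**5. Ibrutinib threshold in protocol 3.1.** 22/28 = 78.6%, and 0.80 × 28 = 22.4, so 22 doses do not reach 80%.

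**The case against.** The best defence is that replaced is simply the protocol's label for not evaluable. Protocol 5.3.6.2 says that patients who meet neither criterion are replaced for the MTD evaluation, and SAP 6.3 echoes that phrase. On this reading SAP 5.2.2, 6.3, 7.4 and 7.5.2 agree, and the SAP says it is based on protocol Section 7, which limits MTD determination to evaluable patients. This is probably what was meant. It does not remove the defect: protocol 3.1 ties replacement to an additional patient, so the literal reading stays open, and the cited section cannot settle it.

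Disclosure would also be fair. SAP 7.1.1 promises an overview of the analysis sets and SAP 7.3 lists all BI 836826 administrations, so a careful reader could largely find such a patient. But the 7.8.1.1 listing covers only replaced patients. Parts of the SAP are absent from the public copy, so this point rests on the sections shown.

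A reader might infer more than the documents support:
- That SAP 6.2 overrides evaluability, because it says "No per protocol set analysis will be performed for this study, hence no patient will be excluded from the analyses". That sentence follows from there being no per-protocol set, and the table beneath it deals with exclusions for protocol violations. Neither defines the MTD evaluation set.
- That the rule allowing escalation on two patients is a main route to the error. Protocol 3.1 applies it when only two patients are evaluable, so the third is already labelled non-evaluable.
- That one patient would reverse the 0.25 overdose test or the 0.50 MTD criterion. The number of crossings depends on the interaction form (9 of 17 states cross 0.25 under the product form and 4 under the printed one; 2 and none cross 0.50). Every tabulated next dose lies below 0.25 by construction, several values sit close to the limits, and no escalation decision remains.

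**Conclusion.** The wording defect is certain: membership of the primary DLT and MTD set rests on an operational event, and the reference given for the rule is wrong. The consequence is conditional. It needs an under-exposed, DLT-free patient without a replacement, which the recruitment stop makes possible but no document shows. If every non-evaluable patient was replaced, nothing changes.

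Given one such patient in the last cohort, the reported overdose probability would typically be about 0.03 to 0.09 too low. This assumes the Table 7.1:3 priors and the inferred interaction; the protocol's own table supports the direction without either.

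A reader might infer that dosing was affected. The documents do not support that: protocol 3.1 governs the cohort decisions, development is discontinued, Amendment 1 says the trial stops before the MTD is reached, and the report is abbreviated. The effect is on reporting only. Severity: minor.

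**What to change.** In SAP 6.3, 5.2.2 and 7.5.2, define the MTD evaluation set as patients with at least one BI 836826 dose who either had a DLT in the MTD evaluation period or met the minimum exposure of protocol 3.1 and 5.3.6.2, whether or not a replacement was enrolled. Use the same term in 7.4. Replace the reference to protocol 3.3.4.1 with 3.1 and 5.3.6.2. Widen the 7.8.1.1 listing to all dosed patients outside the set, with the reason for each.

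Separately, the percentage and the dose count for ibrutinib in protocol 3.1 must be reconciled.

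The SAP cost is wording in four sections, one cross-reference and a wider listing, with no new data.

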## **6.5 POOLING OF CENTRES**

This section is not applicable since there will not be any inferential statistical analysis. Thus, no statistical model in which centre or country is included as factor is applied.

## **6.6 HANDLING OF MISSING DATA AND OUTLIERS**

Missing or incomplete AE dates are imputed according to BI standards (3).

In general, missing data not discussed in (3) will not be imputed unless required for the following analyses and definitions. Then the rules as described below apply.

### **1) Change of laboratory values from baseline**

Laboratory values at baseline: For missing laboratory data at visit 1 (before the first administration of BI 836826) the data of preceding visits will be used.

### **2) Definition of on-treatment period and actual treatment**

Date of permanent discontinuation of last study medication: All reasonable efforts should be undertaken during the study to obtain the dates of permanent discontinuation of last study medication. However, if the date of the very last administration is missing this will be imputed with:

- If only month and year are given, the last day of the month will be used for imputation
- If only the year is given, the 31st of December of this year will be used for imputation

If the imputed date leads to a date that is later than the date of the end of treatment (EOT) visit, then the imputed date is the date of the EOT visit. If the imputed date leads to a date that is later than the death date, then the imputed date is the date of death.

## **6.7 BASELINE, TIME WINDOWS AND CALCULATED VISITS**

Study days and visits will be labelled according to the flow chart of the CTP.

Unless otherwise specified, baseline is defined as the time-point closest to but prior to first administration of BI 836826. If no time is specified and the date is the same as the first administration date, then it will still be considered baseline if not specified otherwise.

Laboratory values: Baseline is defined as the latest time-point before the very first administration of BI 836826. For laboratories where not only the examination date but also time are recorded, examination time has to be taken into account when defining baseline. That is, a laboratory value on the same date as the first administration of BI 836826 is considered as baseline value if and only if the time of laboratory value is before or the same as the time of BI 836826 administration.

## **7. PLANNED ANALYSIS**

For End-Of-Text tables, the set of summary statistics is: N / Mean / standard deviation (StD) / Min / Median / Max. For tables that are provided for endpoints with some extreme data, median, quartiles and percentiles should be preferred to mean, StD, min, and max. Efficacy data are presented by dose cohort. Displays of safety data will be presented by dose cohort and in total.

For time-to-event analysis tables, the set of statistics is: number of patients [N(%)], Number of patients with event [N(%)], <Time to event> [months] followed by P25 (25th percentile), median, P75 (75th percentile), Number of patients censored [N(%)]. If not specified otherwise, the duration as well as the time to event will be displayed in days.

If not otherwise specified, the abbreviation Pxx should be used for displaying the xxth percentile.

Tabulations of frequencies for categorical data will include all possible categories and will display the number of observations in a category as well as the percentage (%) relative to the respective treatment group (unless otherwise specified, all patients in the respective patient set whether they have non-missing values or not). Percentages will be rounded to one decimal place. The category missing will be displayed only if there are actually missing values. The denominator of the main categories is defined by the number of patients in the used patient set. The main categories define the denominators of the subcategories. Subcategories should be intended and “[N(%)” will be displayed only for the main category. If a table includes only categorical data, “[N(%)” is to be displayed in the column header.

Abbreviations (e.g. Wors.) should not be displayed without any explanations. They will be either spelled out in the table or explained in footnotes (whatever is more reasonable from the programming point of view).

If applicable, conversion from days to weeks, months and years will be as follows:

- Weeks = Days/7
- Months = (Days × 12)/365.25
- Years = Days/365.25

### **7.1 DEMOGRAPHIC AND OTHER BASELINE CHARACTERISTICS**

Descriptive statistics are planned for this section.

#### **7.1.1 Disposition of patients**

For patient disposition the standard descriptive table will be populated. Additionally, patients with discontinuations by initial treatment and the reasons will be listed. An overview table with respect to analysis sets (as defined in [Section 6.3](#)) will be provided.

#### **7.1.2 Important protocol violations**

The number of patients with important protocol violations will be displayed.

### **7.1.3 Demographic and other baseline characteristics**

Standard descriptive analysis and summary tables for all patients treated by initial treatment will be created for demography, oncology history, virology, physical examination (including constitutional symptoms), eastern cooperative oncology group (ECOG) performance score, tumour size, previous therapies and previous stem cell transplantations.

## **7.2 CONCOMITANT DISEASES AND MEDICATION**

Descriptive statistics are planned for this section of the report.

Concomitant diseases will be coded similarly as adverse events based on the most current MedDRA version. Concomitant therapies (CTh) will be coded according to the World Health Organisation Drug Dictionary (WHO DD). They will be classified according to the Anatomical, Therapeutic, Chemical (ATC) classification system. The third ATC level will be used to categorise CThs by therapy type. In situations where a medical product may be used for more than one equally important indication, there are often several classification alternatives. As appropriate, patients receiving CThs with more than one possible ATC level-three category will be counted more than once; footnotes will clarify this possible double counting in tables.

Summaries will be presented for previous and concomitant medications started at baseline and for concomitant therapies started after first administration of BI 836826. Transfusions will be displayed separately.

